Our **long-term goal** is to develop interventions to increase perceived self-efficacy (PSE), perception of ability, for CRF self-management as a means of improving functional status and quality of life for persons with NSCLC.²⁵ Our **objective** in this application is to determine the efficacy, optimal timing of initiation, and sustainability of our 6-wk home-based exercise intervention. The **significance** of this study is that it targets two of the most troublesome unmet needs, fatigue and lack of exercise, in an understudied, vulnerable population with the potential to **transform** the current standard of care by providing a rehabilitative exercise intervention after surgery. The proposed research advances the field by providing both an intervention for CRF self-management and evidence for its optimal initiation and sustainability, which currently does not exist for the post-thoracotomy NSCLC population. Our exercise intervention is guided by a theoretical approach (tested by the PI) incorporating self-efficacy theory to strengthen a person's ability to manage their CRF and walking ability.^{17,26} The exercise intervention is **innovative** in its timing and approach in providing self-paced exercise to a vulnerable post-surgical NSCLC population upon discharge from the hospital. The Nintendo's Wii Fit Plus is used to provide light-intensity, virtual reality walking and balance exercise that departs from the status quo and transcends barriers to exercise, as demonstrated by our R21 RCT retention and adherence outcomes.

This study employs a three-arm RCT for persons undergoing NSCLC surgery with participants being randomly assigned to an immediate (post-hospital discharge) exercise intervention group, a wait-list control group (6 wks usual care [wks 1-6] and 6 wks exercise [wks 7-12]), or a 6 wk attention control group (wks 1-6).

Protocol Version 4.0 (7/19/2023). UNMC IRB 560-18 EP. Contact PI: [name] [name], RN.

Primary Outcome: Cancer-Related Fatigue (Severity and Fatigability).

Secondary Outcomes: Severity of Other Symptoms; PSE for CRF Self-Management, Walking, and Balance; Functional Performance; and Quality of Life (QOL).

Aim 1: Determine efficacy of three groups by comparing: 1) immediate exercise intervention group; 2) a wait-list control group; 3) an attention control group by age. Hypothesis 1: The exercise intervention group will outperform wait-list and attention control on all primary and secondary outcomes at wk 6 for all ages.

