Aim 2: Determine efficacy of initiating the exercise intervention 6 wks post-discharge and compare results with the immediate intervention group by age. Hypothesis 2: The immediate exercise intervention group will improve for all ages at a greater rate and magnitude than the wait-list group for all outcomes.

Aim 3: Determine the immediate exercise intervention's sustainability by analyzing a) rates of extension, adherence, and retention; b) acceptability; and c) efficacy of primary and secondary outcomes. Hypothesis 3: The exercise intervention will be acceptable with >50% extending at wk 6 and >70% adherence and retention at wk 12, with improved primary and secondary outcomes at wk 12.

IMPACT: Our results will provide a novel, practical, portable, low-cost, and enjoyable exercise intervention with important information on its optimal timing and sustainability to fill the gap regarding approaches that are applicable to nearly all post-thoracotomy lung cancer patients for reducing CRF severity and fatigability.^{20,22,27-32}

Section 2.0 Introduction

Significance

2A) OVERALL SCIENTIFIC PREMISE

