Fatigability (fatigue with activity, indicator of functional capacity) was measured by the 6-min walk test (6MWT) pre-surgery and post-study, by assessing fatigue reported during the 6MWT and distance walked in 6 mins.¹¹⁰ The IG's wk 6, post-study fatigability decreased from pre-surgery while the UCG's *increased*. IG's fatigue during 6MWT (0-10, 10= most severe) decreased from pre-surgery (M=2.0, SD 1.7) to post-intervention (M=0.4, SD 0.8) while their distance walked increased by a mean of 15% (SD 15). Conversely, the UCG's fatigability *increased* as their 6MWT fatigue increased from pre-surgery (M=1.5, SD 1.8) to post 6 wks (M=3.1, SD 1.5) while their distance walked decreased by a mean of 21% (SD 19). The difference between the IG and UCGs' fatigue during the post-study 6MWT was significant [t (50.9) = -9.3, p<.001; 95% CI -3.3 to -2.1; d = 1.8] as was % change in distance walked post-study vs. pre-surgery 6MWT [t (70) = 9.0, p < .001; 95% CI 28 to 44; d = 1.9].

[figure not shown]

Figure 7. Physical and Mental Health Component Summary SF-36 (60 = Greater Mental/Physical Health)

15 Other symptoms' (not including fatigue) frequency, severity, and interference levels were measured using the M.D. Anderson Symptom Inventory.¹¹¹ Fig 6 shows number, severity, and interference from pre-surgery to wk 6, post-study for IG and UCGs. **Mean # symptoms** reported by the IG decreased from 8.4 (SD 2.4) post-surgery to 4.6 (SD 3.2) at wk 6 post-study, while the UCG reported a mean of 6.6 (SD 3.3) post-surgery and increased to 7.4 (SD 3.3) at wk 6, post-study, a significant difference between groups at wk 6 [t (70) = -3.7; p<.001; 95% CI -4.4 to -1.3; d = 0.9]. Likewise, **mean symptom severity** of the IG was 4.7 (SD 1.5) post-surgery and decreased to 2.1 (SD 1.0) at wk 6, while the UCG started equivalent to the IG post-surgery at a mean severity of 4.9 (SD 1.6) and only reduced to a mean level of 3.8 (SD 1.5) by wk 6, a significant difference between groups at wk 6 [t (61.2) = -5.6; p<.001; 95% CI -2.3 to -1.1; d = 1.1].

For **mean symptom interference**, the IG reported post-surgery mean interference of 3.3 (SD 2.1) decreasing to a level of 0.5 (SD 0.8) at wk 6, while the UCG reported a post-surgery mean interference of 4.5 (SD 2.8) and improved to an interference level of 2.9 (SD 2.3) at wk 6, a significant difference between groups at wk 6 [t (41.8) = -6.0; p< .001; 95% CI -3.2 to -1.6; d = 1.1].

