
Exclusion Criteria. 1) Severe impairment of sight, hearing, speaking; 2) Active treatment for malignancy within past 3 months (other than non-melanoma skin cancer or long-term hormonal treatment for common cancers such as breast and prostate if disease is stable); 3) Weight greater than 330 pound (weight capacity of the Wii balance board); 4) History of photosensitive seizures; 5) Any condition or disorder that would impede safe participation as directed; and 6) Plans to relocate outside the area during the study period or unable to fully participate.

Section 4.0 Registration Procedure

Random Assignment. Randomization will be implemented after consent and before surgery. A random number table generated by our statistician will assign the participant to the IIG, WCG, or ACG. Blocking factors in the randomization scheme include participant's age (< 65 or ≥ 65 years) and functional capacity level (6MWT distance ≥ 452 meters).

Blocking Factors in the Randomization Scheme. Randomization will be implemented after consent and participants will be assigned to IIG, ACG, or WCG. This gives all participants an equal chance of being assigned to one of the three study groups. Blocking factors used successfully in the randomization scheme of our two-arm RCT (R21 CA164515) include the participant's age (≤ 64 years or ≥ 65 years) and functional capacity level (those that achieve six minute walk test [6MWT] distance ≥ 452 meters). This is based upon the work of our oncology exercise consultant, [name], who found for persons with NSCLC that the 6MW distance provides important objective prognostic information relative to survival in that 452 meters was found to be the minimum distance achieved for those in the high capacity functioning group.

Figure 8. Study Design (N=180)		Pre-surgery	Surgery	Post-surgery	Weeks 1-6		Weeks 7-12	
R	Immediate Intervention Group (IIG n=60)	B, S	H	D, V	D, V, —————>	S	D, —————>	S
R	Wait-list Control Group (WCG n=60)	B, S	H	D	D, Usual Care	S, V, D	D, V, —————>	S
R	Attention Control Group (ACG n=60)	B, S	H	D	D, Attention Control	S		

R=random assignment, B=baseline data collection, S=six-minute walk test administered, H= hospital visit, V = home visit, —————> = exercising, D=data collection

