
Section 5.0 Research Design

5A) Introduction to the Research Design of Proposed Project

We propose a three-arm, repeated measures RCT for persons undergoing NSCLC surgery as shown in **Fig 8**. The design provides for **efficacy** comparisons of outcome measures among the immediate (exercise) intervention group (IIG), the wait-list control group (WCG) usual care, and the attention control group (ACG) by age after 6 wks (**Aim 1**) through the measurement of primary and secondary outcomes. The design also provides for evaluation of the timing of the intervention (**Aim 2**) by comparing study outcomes of the IIG's wks 1-6 with those of the WCG's wks 7-12 by age to account for time since surgery. Note that the timing of the data collection occurs near the time of the assessment during the week when the assessment is conducted. For example, if a participant has an unexpected visitor at their home and would like to have the data collector call the next day, then the data collector may call the next day. Unlike mice or non-human studies, we need to balance absolute timing against the needs of our human participants so we incorporate some flexibility required of our human participants when collecting data. Determining optimal timing to initiate an exercise program for post-surgical NSCLC patients is needed. We chose to start the WCG intervention at 6-wks post-hospital discharge based on Leach et al.'s¹¹³ findings that 43% of the 66 postsurgical NSCLC patients in their study preferred to start an exercise program during adjuvant treatment. Also, adjuvant treatment (radiation and/or chemotherapy) commonly begins 4-10 wks after surgery, with nearly 30% of patients undergoing adjuvant treatment¹¹⁴ Sustainability of the intervention (**Aim 3**) can be determined by offering the IIG the option to extend their exercise to 12 wks and calculating the percent that elect to extend, assessing acceptability, adherence, and retention while measuring primary and secondary outcomes for efficacy. Adverse events will be monitored to provide for safety (R21 RCT reported no adverse events).

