Perceived Self-Efficacy	CRF and Walking Self-management	PSE for Fatigue Self-Management (6 items), Walking Duration (12 items)	Pre & Post-Surgery Weeks 1-12	PSE for CRF self-management (.92) and PSE for walking duration (.95).
Perceived Self-Efficacy	Balance	Activities-specific Balance Confidence (16 items)	Pre & Post-Surgery Weeks 3, 6, 9, 12	PSE for balance for increasingly challenging activities (.82-.90).
CRF Self-Management Behaviors	Walking Exercise	Recorded in Daily Diary and electronically in the Wii Fit Plus	Weeks 1-12	Total number of minutes walked with the Wii per week.
CRF Self-Management Behaviors	Balance Exercise	Recorded in Daily Diary and electronically in the Wii Fit Plus	Weeks 1-12	Total number of balance exercises completed with the Wii per week.
Functional Status	Capacity	Fatigability; Six-minute Walk Test	Pre-Surgery, Prior to Chemo/Week 6, & 12	Degree of fatigue associated with walking during the six-minute walk test. Distance walked in six minutes.
Functional Status	Performance	SF-36 v2 – 8 subscales accounting for two components, physical and mental health (36 items)	Pre & Post-Surgery Weeks 3, 6, 9, 12	Performance of daily mental and physical activities that people do in the normal course of their lives (.78-.92)
Functional Status	Performance	Pedometer Daily Diary	Weeks 1-12	Performance in average number of steps taken per day per week
Quality of Life	Quality of Life	QOL Index: Overall QOL, Family, Health/Function, Socioeconomic, Psych/Spiritual (66 items)	Pre & Post Surgery Weeks 3, 6, 9, 12	Satisfaction with various aspects of life and the importance of each aspect of life to the person (.73-.99)

Legend: Surgery = Sx; CRF = Cancer-Related Fatigue. PSE = Perceived Self-Efficacy. Medical Outcomes Short Form-36 v2 = SF-36 v2. QOL = Quality of Life

Revision 5/19/2019. Updated Table with the following 3 measures added.

Table 3. Main Concepts, Variable, Measures, Collection Schedule, and Measurement Objective

Concept	Variable	Measure # Items	Schedule	Measurement Description (Cronbach's alpha)
Symptoms	Sleep Impairment	PROMIS v 1.0 Sleep-Related Impairment Short-Form 8a (8 Items)	Pre & Post-Surgery Weeks 3, 6, 9, 12	Degree of sleep-related impairment. (0.90)
Symptoms	Pain Source, Pain Treatment, Severity and Interference Information	The Brief Pain Inventory (4 Severity Items; 7 Interference items; 4 Source Items)	Pre & Post-Surgery Weeks 3, 6, 9, 12	Degree of pain severity and impact of pain on every day. living. (0.77 to 0.91)

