Perceived Self-Efficacy	Pain Self-Management	The Perceived Self-Efficacy for Pain Self-Management Inventory (6 Items)	Pre & Post-Surgery Weeks 3, 6, 9, 12	Degree of pain self-management. (0.90)

Aim 2 – Measures – WCG Delayed Intervention. At the start of wk 7, WCG will begin the intervention, concluding at wk 12. Aim 1 study variables and measures (Table 3) will be analyzed for Aim 2 for wks 7-12 to compare with the IIG wks 1-6 outcomes.

Aim 3 – Measures – IIG Intervention Sustainability. At the start of wk 7, IIG participants will be given the option to extend the intervention an additional 6 wks. We will measure the extension rate as % participants who elect to extend. Adherence to the intervention will be measured as % participating in the intervention who adhered to prescribed intervention. Weekly adherence will be calculated by taking number of times prescribed intervention was completed divided by total number of interventions prescribed for week. These data are recorded in the Daily Diary and will be confirmed by research staff reviewing recorded data in Wii Fit-Plus. Retention, measured as part of sustainment, will be calculated as % who elected to extend 6 wks who completed final data collection at wk 12. Based on our conceptual definition of sustainability, we will measure the extent to which components of the intervention were rated acceptable for continued use by participant. Acceptability will be measured at end of wk 6 and 12 using a 15-item Acceptability Questionnaire (Appendix B1) using a numeric scale (1 to 6: 6 = agrees strongly) with higher scores indicating greater acceptability of the exercise program. The Questionnaire has a Flesch-Kinkaid 6th grade reading level and was successfully used in our R21 RCT and allows participants to rate how well barriers and facilitators to exercise are addressed. Open-ended questions provide further input.^{23,24} Efficacy will be measured using the same study variables and measures analyzed in Aim 1 (Table 3) for wks 7-12.

Section 8.0 Drug Formulation and Procurement

Not applicable. This study is not a pharmaceutical trial.

Section 9.0 Toxicity and Adverse Event Reporting Guidelines

Study Monitoring

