AEs will be collected from the time the subject signs the consent form until 30 days after the final protocol specified intervention. All AEs will be followed until resolution or a cause is identified. AEs judged by the investigator as not related or probably not related to the treatment will NOT be followed beyond the end of the study.

Section 10.0 Statistical Considerations

Statistical Analysis. All tests of hypotheses will be two-tailed at $\alpha=0.05$. We compare groups at baseline using parametric and non-parametric tests to assess equivalence of confounding physiological and contextual patient characteristics, and pre-surgical outcome variables. If substantive differences exist, they will be controlled for in subsequent analyses by regression techniques, guided by the degree of dissimilarity rather than strict statistical significance.¹⁴⁴

Primary analysis (Aim 1) is the comparison among study groups of the primary outcome CRF severity and fatigability assessed at approximately 6 wks post-surgery. Analysis is based on a regression model for both CRF scores with the following variables in the regression equation: baseline CRF, study group, age, and (if appropriate) plausible interaction between these variables. We test association of study group with outcomes.

In Aim 2 our hypothesis comparing outcomes in IIG and WCG by age group will be addressed in the context of a longitudinal analysis. There are 6 time-ordered differences between IIG and WCG. We use generalized linear (mixed) models to allow flexible correlation structures in the repeated measures.^{145,146} Our regression equation has in addition to the aforementioned variables: time (week) of assessment, and critically, study group with time interactions. The model allows us to test if group effects are changing over time – referred to as a “parallel” profile analysis.¹⁴⁷ If the hypothesis is supported, we test whether that average profiles (over time) in

the two groups are the same. Aim 3 concerns three binary responses in the IIG group at 6 wks: extension, retention, and adherence. Logistic regression models will be used to assess the influence of explanatory variables on the likelihood of outcome.¹⁴⁷⁻¹⁴⁹

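### Aim 2 cannot test a greater rate of improvement for fatigability, a primary outcome, because the schedule gives only one matched walk test per arm

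*Combined protocol and SAP*

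**What the plan says.** Section 1.0 (Hypothesis 2) states that the IIG "will improve for all ages at a greater rate and magnitude than the wait-list group for all outcomes". The same section names fatigue severity and fatigability together as the primary outcome.

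The alignment is given twice. Section 5A describes Aim 2 as "comparing study outcomes of the IIG's wks 1-6 with those of the WCG's wks 7-12". Section 7.0 says the Table 3 measures "will be analyzed for Aim 2 for wks 7-12 to compare with the IIG wks 1-6 outcomes".

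Section 10.0 gives a single Aim 2 analysis. It states "There are 6 time-ordered differences between IIG and WCG" and adds week and group-by-week terms to the baseline-adjusted model. It tests whether the two profiles are parallel and then whether their average levels agree. No separate Aim 2 method is given for outcomes collected less often than weekly.

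Section 7.0 defines fatigability as the fatigue rating for the six-minute walk divided by walking velocity, so it has a value only when a walk is done. Table 3 schedules the walk at "Pre-Surgery, Prior to Chemo/Week 6, & 12". Figure 8 (key: "S=six-minute walk test administered") agrees. Both arms walk before surgery, at the end of weeks 1-6 and at the end of weeks 7-12. In the WCG the middle walk follows usual care and precedes exercise.

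**The concern.** A claim about rate needs at least two time points within the exercise period in each arm, on a common clock. Weekly scales meet that easily. Fatigability does not: each arm has one walk after exercise has begun, and only the WCG has a walk at the start of its exercise period.

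If the text stays as it is, Aim 2 promises a conclusion about a primary outcome that the schedule cannot deliver. The analyst would then have to improvise. The obvious improvisation, change over each exercise period, would compare unlike quantities: the IIG change would run from before the operation, and the WCG change from six weeks after discharge.

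**Working it through.** **Inputs.** Assessment weeks from Table 3 in Section 7.0, including the three scales added in 2019; walk times from Figure 8; alignment from Sections 5A and 7.0. IIG week k is matched with WCG week k + 6.

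**Step 1: reproduce the plan's figure.** For a measure taken weekly in weeks 1-12, k runs from 1 to 6, which gives 6 differences. The stated figure is correct for these measures.

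**Step 2: repeat the count for each outcome.** With T matched times, a parallel-profile test has T − 1 degrees of freedom.

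| Outcomes | Weeks, IIG / WCG | T | T − 1 |
|---|---|---|---|
| Brief Fatigue Inventory, symptom inventory, self-efficacy for fatigue, self-efficacy for walking, pedometer steps | 1-6 / 7-12 | 6 | 5 |
| Balance confidence, SF-36, QOL Index, sleep impairment, pain, pain self-efficacy | 3, 6 / 9, 12 | 2 | 1 |
| Fatigability (six-minute walk) | 6 / 12 | 1 | 0 |

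The six scales in the second row also have a start value in each arm: the post-surgery assessment in the IIG and week 6 in the WCG.

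**Step 3: check whether the rate term can be estimated.** Take a model with intercept, group, linear time since the start of exercise, and group × time: four parameters.

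- With six or two matched times per arm, the design matrix has rank 4 of 4, so the interaction can be estimated.
- Fatigability at matched times has two distinct rows, (1, 0, 6, 0) for the WCG and (1, 1, 6, 6) for the IIG. The rank is 2 of 4.
- Adding the WCG's week-6 walk as its start value contributes (1, 0, 0, 0). The rank rises to 3 of 4. The WCG slope can then be estimated, but the IIG slope cannot, so their difference cannot either.

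**Step 4: what remains for fatigability.** The difference in level between IIG week 6 and WCG week 12 can be estimated and adjusted for the pre-surgery walk that both arms have. That is a test of magnitude.

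**Step 5: why change over each exercise period is no substitute.** The IIG change would be week 6 minus pre-surgery and would contain the operation. The WCG change would be week 12 minus week 6 and would not. The pilot (Section 2N) gives a possible order of size: under usual care, walk fatigue went from 1.5 to 3.1 (3.1 − 1.5 = +1.6 on a 0-10 scale) and distance fell by 21%. These are net changes from pre-surgery to week 6. They mix the operation with six weeks of unaided recovery, so they do not isolate the surgical loss. Nor are they the trial's fatigability ratio.

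**The case against.** The strongest reply has four parts.

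- **Six is right where it matters most.** It is correct for fatigue severity, the other primary outcome, and the sentence in Section 10.0 does not itself say that it covers every outcome. This stands. The difficulty comes from reading that sentence with Hypothesis 2, which does cover all outcomes, when no other Aim 2 method is given.
- **The less frequent scales are not lost.** A reader might infer that every outcome without weekly data must leave the rate claim. The documents do not support that. Two matched assessments allow a test on 1 degree of freedom, and both arms have a start value as well.
- **No biased analysis is written down.** A reader might infer that the plan charges the surgical loss to the IIG alone. It does not. Section 10.0 specifies no change score, and its Aim 2 model carries the baseline covariate. With a pre-surgery baseline in both arms, IIG week 6 and WCG week 12 both lie after surgery. The bias would arise only if an analyst computed change over each exercise period.
- **A calendar-time analysis can be fitted.** Comparing both arms at weeks 6 and 12 gives rank 4 of 4. But that is not the Aim 2 contrast. Week 6 repeats Aim 1, and at week 12 IIG exercise has been optional for six weeks, with Section 10.0 making the 12-week models conditional on electing to extend.

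The walk label also allows a test before chemotherapy in place of week 6. That could move the walk earlier for some patients, but it gives the IIG no common value at the start of exercise.

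**Conclusion.** The point holds for fatigability. Under the stated alignment it has 1 matched difference and 0 degrees of freedom for the parallel-profile test, so the rate half of Hypothesis 2 cannot be tested for one of the two primary measures. Magnitude can be. For six further scales the correct count is 2, which limits the rate test without removing it. For the five weekly measures the plan is right as written.

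This rests on reading rate as the group-by-time term, which is how Section 10.0 sets up its test, and on the walk schedule in Table 3 and Figure 8. Aim 1 is unaffected. It would go too far to say that Aim 2 as a whole fails, or to treat the pilot's usual-care changes as a measured surgical loss.

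**What to change.** 1. In Section 10.0, replace the single figure of six with the number for each outcome: six for the five weekly measures, two (plus a start value in each arm) for balance, SF-36, QOL, sleep, pain and pain self-efficacy, and one for fatigability.
2. In Hypothesis 2, remove fatigability from the claim about rate and keep it in the claim about magnitude.
3. Specify the Aim 2 test for fatigability as IIG week 6 against WCG week 12, each adjusted for the pre-surgery walk. State that change over each exercise period will not be used, because it would span the operation in one arm only.
4. Label any comparison of both arms at week 12 as supplementary, because IIG exercise in weeks 7-12 is optional and the 12-week models are conditional on extension.

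The cost is wording in Sections 1.0 and 10.0, with no new data. The downside is that no conclusion about rate is drawn for fatigability, which the schedule could not support in any case.
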